Attachment 4: Amendment 1 changes**Amendment 1** (7 April 2016)

This amendment is considered to be nonsubstantial based on the criteria set forth in Article 10(a) of Directive 2001/20/EC of the European Parliament and the Council of the European Union, in that it does not significantly impact the safety or physical/mental integrity of subjects, nor the scientific value of the study.

The overall reason for the amendment: The overall reason for the amendment is to address the feedback received from Investigators.

| Applicable Section(s) | Description of Change(s) |
|--|--|
| Rationale: | Clarification of study design, simplification of study conduct, to enhance enrollment and data collection and also to avoid scheduling difficulties (in response to comments from investigators in attendance). |
| Synopsis Overview Of Study Design; Time And Events Schedule, Part A and Part B | The window of administering rivaroxaban for subjects in Part A and Part B for 12 days was increased from 6 days to 9 days, to allow for sufficient time to complete this visit/phone call. |
| Synopsis, Subject Population; Section 4.2 Exclusion Criteria | Exclusion criterion #1: Clarified that the screening transthoracic echocardiogram to rule out thrombosis needs to be post-Fontan. Exclusion criterion #4: Current chest-tube placement was deleted as an example of high risk for bleeding qualifying for exclusion. Exclusion criterion #6: Deleted 'Indication'. Exclusion criterion #7: To align with global practices, study participation exclusion limit of platelet counts at screening was changed from less than $100 \times 10^9/L$ to less than $50 \times 10^9/L$. |
| Time And Events Schedule, Part A and B, Screening Period | Footnote regarding the screening period was added to also allow for local reading of the subjects' transthoracic echocardiogram to rule out thrombosis. In addition, if subject is enrolled, instruction was added to send the transthoracic echocardiogram also to the core laboratory. Clarification was provided that adverse event assessment includes a review of all ongoing and new adverse events. For Hematology, serum chemistry, PT, and aPTT testing at screening, clarification was added that either hospital laboratory, local laboratory results or central laboratory results are acceptable. |
| Section 1.1.5, Efficacy and Safety Profile Based on Pediatric Clinical Studies | The section was updated with a more current cut-off date on the status of enrollment and overall safety assessment. |
| Section 1.2, Comparator Agent | References to the PI and SmPC for ASA were replaced with reference to the local approved product label. |
| Synopsis, Section 6, Dosage and Administration | Minor edits for ASA tablet. Instructions were added regarding handling a missed morning and evening dose of rivaroxaban and ASA. |
| Section 9.1.2 Screening Period | Clarification was added that the screening visit will take place after the Fontan procedure. |

| Applicable Section(s) | Description of Change(s) |
|--|--|
| Synopsis, Overview Of Study Design, Early Study Medication Discontinuation; Section 3.1. Overview of Study Design; Section 9.1.5. Posttreatment Period (Follow-Up Contact); Section 10.2.2. Permanent Discontinuation of Study Drug; Section 10.3. Withdrawal From the Study | Instructions were added regarding the follow-up of subjects who were reported by the core laboratory to have an event on the Screening transthoracic echocardiogram. |
| Section 9.1.6, Transthoracic Echocardiograms | For the Screening post-Fontan transthoracic echocardiogram, instructions were added to allow local reading to meet the inclusion criteria for enrollment and additional evaluation by the core laboratory if subject is enrolled. |
| Section 9.2. Pharmacokinetics/Pharmacodynamics Evaluations Part A | Procedure of sending blood samples to the central laboratory was simplified by limiting it to after the collection of the last sample on Day 4 only. |
| Section 9.3.2, Approach to the Subject with a Bleeding Event | Clarified that it is the treating physician who could consider the measures provided to treat a serious bleed. Clarifications for parents/ legally acceptable representatives were added if the subject has signs and symptoms of clinically significant bleeding. |
| Section 9.4. Efficacy Evaluations/Outcomes | Further clarification was added regarding the adjudication procedure by the CIAC and responsibility of sites to compile the adjudication package. |
| Section 9.6. Study Booklet | More information was added related to the packaging and storage of rivaroxaban and comparator ASA. |
| Section 10.2.2. Permanent Discontinuation of Study Drug | Persistent noncompliance was added as an example of safety reasons for study treatment discontinuation. |
| Section 10.3. Withdrawal From the Study | Additional reasons for withdrawing a subject from the study were added. |
| Section 11.5 Efficacy Analysis | To clarify the analysis set in which the efficacy analyses will be performed. |
| Section 12.3.2. Serious Adverse Events | To clarify the current company-wide clinical study conduct processes to transmit initial and follow-up reports of a serious adverse event. |
| Section 14.1. Physical Description of Study Drug(s) | Minor edits for ASA tablet. |
| Section 14.2, Packaging | Minor edits were made. |
| Section 14.4. Preparation, Handling, and Storage | Minor edits were made. |
| Section 15. Study-Specific Materials | Recruiting tools were edited to 'Sponsor-approved subject recruiting materials'. Use of an iPad was added to study management tools provided to the investigator. |
| Section 16.1 Study-Specific Design Considerations; Attachment 1, Volume of Blood to be Collected | Clarified that the blood volume estimates do not include any blood discarded, as these volumes may differ from site to site. |

| Applicable Section(s) | Description of Change(s) |
|--|--|
| Section 17.4. Source Documentation; Section 17.5. Case Report Form Completion; Section 17.9.1. Study Completion/End of Study | Changes were made to align wording with current company-wide clinical study conduct processes (use of electronic source system and CRFs). |
| Rationale: The collection of blood samples was further clarified and heparin flushes are to be allowed. Heparin flushes can be used except before PK/PD samples are drawn. These have to be performed with saline to avoid interference with PK/PD results. | |
| Section 9.2. Pharmacokinetics/Pharmacodynamics Evaluations; 9.5 Sample Collection and Handling | Explained procedure for blood sample collection via an indwelling cannula and central line in more detail and heparin flush was allowed, except before collecting PK/PD samples. |
| Throughout the protocol | Minor, consistency and logical clarifications were made throughout the document, which do not affect the overall study concept. |
| References | Addition of 2 references |

INVESTIGATOR AGREEMENT

JNJ-39039039; BAY 59-7939 (rivaroxaban)

Clinical Protocol 39039039CHD3001 - Amendment INT-2

INVESTIGATOR AGREEMENT

I have read this protocol and agree that it contains all necessary details for carrying out this study. I will conduct the study as outlined herein and will complete the study within the time designated.

**ABBREVIATIONS**

ASA	Acetyl Salicylic Acid
aPTT	Activated Partial Thromboplastin Time
AXA	Anti-FXa Activity
CI	Confidence Interval
CIAC	Central Independent Adjudication Committee
CrCl	Creatinine Clearance
DPS	Data Presentation Specifications
DRC	Data Review Committee
EC	Executive Committee
eCRF	Electronic Case Report Form
ESMD	Early Study Medication Discontinuation
IDMC	Independent Data Monitoring Committee
ISTH	International Society on Thrombosis and Haemostasis
IWRS	Interactive Web Response System
KM	Kaplan-Meier
PBPK	Physiologically-based Pharmacokinetic
PD	Pharmacodynamics
PT	Prothrombin Time
PK	Pharmacokinetics
SAP	Statistical Analysis Plan
SC	Sponsor Committee
TE	Treatment-Emergent
TEAE	Treatment-Emergent Adverse Events

---

**SAP AMENDMENT**

SAP Version	Issue Date
Original SAP	November 15 th , 2016
Amendment 1	May 16 th , 2019

The principal rationale for the SAP Amendment 1 is to clarify the definition of the categories and terms of key protocol deviations considered for the Per protocol Set. Also, PK/PD analysis plan in Section 6 was updated to include Part B data, and Attachment 1 was removed because a full PK/PD data analysis plan will be provided separately.

**1. INTRODUCTION**

This Statistical Analysis Plan (SAP) specifies definitions of analysis sets, key derived variables, and statistical methods for analysis of safety and efficacy data, as well as statistical summaries of PK and PD findings for the Phase 3 study 39039039CHD3001 (also known as UNIVERSE). This SAP is based on the Protocol 39039039CHD3001, Amendments INT-1 and INT-2, which were finalized on April 7th, 2016 and July 28th, 2017, respectively. Titles, mock-ups and programming instructions for all statistical outputs (tables, figures, and listings) are provided in a separate document entitled Data Presentation Specifications (DPS).

**1.1 Trial Objectives**

The primary objective of Part A of the study is to characterize the single- and multiple-dose pharmacokinetics (PK) and pharmacodynamics (PD) profiles after oral rivaroxaban therapy administered to pediatric subjects 2 to 8 years of age with single ventricle physiology who have completed the Fontan surgery within 4 months prior to enrollment. The secondary objective of Part A is to assess the safety and tolerability of rivaroxaban treatment.

The primary objective of Part B is to evaluate the safety and efficacy of rivaroxaban, administered twice daily (total daily exposure matched to rivaroxaban 10 mg once daily in adults) compared to acetylsalicylic acid (ASA), given once daily (approximately 5 mg/kg) for thromboprophylaxis in pediatric subjects 2 to 8 years of age with single ventricle physiology who have completed the Fontan surgery within 4 months prior to enrollment. The secondary objective in Part B is to further characterize the PK and PD profiles of rivaroxaban.

## 1.2 Trial Design

[figure not shown]
This is a prospective, open-label, active-controlled, multicenter study designed to evaluate the PK and PD profiles, safety and efficacy of rivaroxaban for thromboprophylaxis in pediatric subjects 2 to 8 years of age with single ventricle physiology who have completed the Fontan surgery within 4 months prior to enrollment.

The two parts of the study are as follows:

- Part A: This is the 12-month, non-randomized, open-label, part of the study which includes an Initial PK, PD and Safety Assessment Period. The Data Review Committee (DRC) will assess by Day 12 the single- and multiple-dose rivaroxaban PK, PD and the initial safety and tolerability data available from each subject, prior to the subject continuing in the study to complete the planned 12 months of open-label rivaroxaban therapy of Part A. Subjects in Part A will not participate in Part B.
- Part B: This is the randomized, open-label, active-controlled part of the study that will evaluate the safety and efficacy of rivaroxaban compared to ASA for thromboprophylaxis for 12 months. Subjects randomized to rivaroxaban will also have PK and PD assessments.

A diagram of the study design is provided below in [Figure 1](#).

Figure 1: Schematic Overview of Study 39039039CHD3001

**Note:** An internal DRC will assess before the Day 12 Visit, the PK, PD, and safety data from each subject, prior to the subject continuing in the study to complete the planned 12 months of open-label rivaroxaban therapy. Enrollment in Part A will end, and enrollment in Part B will start, once the cumulative data from all subjects in the Initial PK, PD, and Safety Assessment Period of Part A are deemed acceptable by the IDMC.

### **1.3 Statistical Hypotheses for Trial Objectives**

There is no formal hypothesis testing for this study.

### **1.4 Sample Size Justification**

A total of at least 100 pediatric subjects overall are planned to be enrolled in this study. Due to the limited availability of the study population and the expected low event rates, this study is not powered to test formal hypothesis for efficacy. The total sample size is based on regulatory feedback to obtain sufficient safety data in this pediatric population.

The sample size of approximately 10 subjects for Part A is considered adequate for the initial PK assessment of rivaroxaban in the studied pediatric subjects. Approximately 90 subjects will be enrolled into Part B of the study.

### **1.5 Randomization and Blinding**

Subjects in Part A will not be randomized.

Randomization in Part B of this study will begin once the cumulative subjects' data from initial PK and Safety Assessment in Part A are deemed acceptable by the IDMC.

Central randomization will be implemented in this study for Part B: approximately 90 subjects will be randomly assigned to 1 of 2 treatment groups based on a computer-generated randomization schedule prepared before the study by or under the supervision of the sponsor; the assignment to treatment groups will be 2 to 1 (rivaroxaban to ASA).

The interactive web response system (IWRS) will assign a unique treatment code, which will dictate the treatment assignment for the subject. The requestor of the treatment code/randomization must use his or her own user identification and personal identification number when contacting the IWRS to receive the relevant subject details to uniquely identify the subject. The study drug number will be assigned and recorded in the IWRS.

As this is an open-label study, blinding procedures are not applicable. Open-label treatment will be used to allow for further evaluation of the PK and PD profiles of rivaroxaban throughout the study.

### **1.6 Interim Analysis and Committees**

No interim analysis is planned to be conducted in this study (PK evaluation in Part A is not considered interim analysis.)

### 1.6.1 Data Review Committee (DRC)

The DRC consists of members from the sponsor not directly involved in the conduct of the study, who will evaluate the PK and safety of each subject in Part A, and who will evaluate that information relative to the physiologically-based pharmacokinetic (PBPK) model predictions. The DRC will assess the PK, PD, and the safety data available from each subject, prior to the subject continuing in the study to complete the planned 12 months of open-label rivaroxaban therapy. The DRC will only operate during the initial PK, PD, and safety assessment period of Part A.

The DRC review package for individual subjects may include the following 3 parts (details are provided in a separate DRC Charter document that details the process of DRC review):

- PK data: rivaroxaban  $AUC_{0-24}$ ,  $C_{max}$  and  $C_{min}$  on Days 1 and 4.
- PD data: PT and aPTT values at baseline and Days 1 and 4; time-matched PT and aPTT versus rivaroxaban plasma concentration plots on Days 1 and 4.
- Safety data: all available subject information including but not limited to demographic information, medical history, baseline lab values, dosing information, adverse events and outcome events (including best available bleeding and thrombotic events).

### 1.6.2 Independent Data Monitoring Committee (IDMC)

The IDMC will evaluate PK, PD, safety and efficacy data to ensure subject safety throughout the study. The IDMC will be an independent expert advisory group external to the sponsor and study. For Part A only, the IDMC will review the cumulative data from the Initial PK, PD, and Safety Assessment Period and will provide the recommendation to the EC and sponsor committee to cease enrollment in Part A and to start enrollment directly into Part B. The IDMC will operate for both Part A and Part B. The acceptability criteria will be described in the IDMC charter.

### 1.6.3 Central Independent Adjudication Committee (CIAC)

The CIAC is comprised of specialist physicians as appropriate and necessary. Committee members do not directly enroll subjects in the study, are not involved in the study monitoring, and do not have direct operational responsibilities for the conduct of the study. Members will review all safety and efficacy outcomes that occur post- enrollment as they become available and

adjudicate and classify the following events in a consistent and unbiased manner according to definitions in the CIAC charter while blinded to treatment assignment:

Safety and efficacy outcomes include bleeding events, any thrombotic event (venous or arterial), other vascular events, and deaths that occur during the study and the 30-day post-study treatment period.

Sites will be required to complete a worksheet, compile an adjudication package, and to send it to the adjudication office within 6 weeks from occurrence of the event. The CIAC procedures will be described in the CIAC charter. Adjudication results will be the basis for the final analyses.

The best available data will be used for DRC and IDMC reviews. The CIAC-adjudicated results will be used in the final analysis for all subjects.

#### **1.6.4 Executive Committee (EC)**

The EC will provide overall academic leadership for the study and will oversee the conduct and the publications of the results. In addition, the EC will receive recommendations from the IDMC regarding modification to the study and will decide whether to accept the recommendations. The EC will have 2 co-chairs and will consist of members of academic institutions and 1 member from the sponsor.

## **2. GENERAL ANALYSIS DEFINITIONS**

Statistical analysis of the overall study data will be done by the sponsor.

Description of the statistical methods to be used to analyze the efficacy and safety data is outlined in this document, including imputation rules for missing or partially missing dates.

Summaries by treatment group using appropriate descriptive statistics will be provided for study variables. Descriptive statistics such as mean, median, standard deviation, 95% CIs (when applicable), minimum, and maximum will be used to summarize continuous variables; Counts and percentages will be used to summarize categorical variables. The Kaplan-Meier (KM) method will be used to summarize time-to-event data. Graphical data displays may also be used to summarize the data.

For analysis purposes, the data from subjects receiving rivaroxaban in Part A of the study will be combined with the data from subjects in Part B of the study randomized to rivaroxaban. The data

will also be summarized separately for subjects randomized in Part B only (rivaroxaban vs. ASA), and for subjects participating in Part A only.

All CIAC adjudicated efficacy and bleeding outcomes will be used in the final analyses.

The statistical evaluation will be performed by using the software package SAS release 9.2 or higher (SAS Institute Inc., Cary, NC, USA).

## **2.1 Definition of Trial Dates**

Trial reference start date is defined as the date on which the first dose of study drug is taken by the subject.

Trial reference end date is defined as the date of the last trial-related procedure for the subject; specifically it is equal to the maximum of the following dates:

- Date of the last study-related visit or phone contact (including scheduled or unscheduled visits)
- Date of the last study-related procedure, finding or event, including, but not limited to, safety and efficacy endpoint events, adverse events, concomitant medications, disposition, and death

First dose date is defined as the date on which the first dose of study drug is taken by the subject. Due to the nature of Part A, the first dose date for Part A subjects will not be allowed to be missing. For Part B randomized subjects, if this date is missing or incomplete for a subject who takes study drug, the first dose date is set to the earliest logically possible date. More specifically, the first dose date is defined as the maximum of the randomization date and the first day of the month if only day is missing; it is defined as the randomization date if day and month are missing.

Last dose date is defined as the date on which the last dose of study drug is taken by the subject. If this date is missing or incomplete for a subject who takes study drug, the last dose date will be set to the latest logically possible date. It will be capped by (that is, taking the minimum with) Day 353 date, death date, trial reference end date, and the upper bound of the logically possible range if partial date is available, and further bounded below by (that is, taking the maximum with) the (imputed) first dose date, any complete temporary drug stop and re-start date, or the lower bound of the logically possible range.

Last efficacy-evaluation date is defined as the date of the last study visit at which the outcome status of efficacy endpoints is evaluated – Month 12 or ESMD visit.

Planned treatment end date: 12 months since randomization or enrollment for each subject. The planned treatment end date varies for subjects depending on their randomization or enrollment date.

## **2.2 Analysis Sets**

Full Analysis Set: This analysis set consists of all subjects in Part A who receive at least 1 dose of study drug and all subjects in Part B who are randomized and receive at least 1 dose of study drug.

Safety Analysis Set: This is the same as Full Analysis Set.

Per-protocol Set: The per-protocol set will exclude subjects with key protocol deviations from full analysis set. These deviations will include the following:

- Not meeting the following key inclusion or exclusion criteria:
  - INT-1: inclusion criteria 1, exclusion criteria 1, 4, 6 (> 90 consecutive days), 7, 8, 13, 14, 15, 18
  - INT-2: inclusion criteria 1, exclusion criteria 1, 4, 6 (> 90 consecutive days), 7, 8.1, 13, 14, 15, 18
- Taking incorrect study drug
- Not discontinuing study drug permanently according to the protocol
- Having been taking prohibited concomitant therapies as specified in the protocol

PK Analysis Set: All subjects who receive at least 1 dose of study drug and have quantifiable rivaroxaban plasma concentrations will be included in the descriptive PK analysis.

PD Analysis Set: All subjects who receive at least 1 dose of study drug and have quantifiable and time-matched PT, aPTT, and/or anti-FXa activity values will be included in the descriptive PD analysis.

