9.1.6. Transthoracic Echocardiograms

Transthoracic echocardiograms will be obtained according to the timepoints noted in the Time and Events Schedule for the assessment of thrombotic events. For the Screening post-Fontan transthoracic echocardiogram, the Post-Fontan Echocardiographic Examination protocol in [Attachment 2](#) is to be followed, and the following guidelines will be applicable:

- The subject is not to be enrolled if local reading of the Screening transthoracic echocardiogram confirms thrombosis. The subject's transthoracic echocardiogram will not need to be sent to the core laboratory.
- The subject may be enrolled if local reading of the Screening transthoracic echocardiogram rules out thrombosis and the remaining inclusion/exclusion criteria are satisfied. The Screening transthoracic echocardiogram is to be sent to the core laboratory for central reading.
- The subject will be withdrawn from the study if the subject is enrolled after local reading rules out thrombosis on the transthoracic echocardiogram and subsequently central reading by the core laboratory reports a thrombosis from the same transthoracic echocardiogram. The reasoning for the early withdrawal will be documented on the eCRF.

The core laboratory report will serve as the baseline for the comparison of the subsequent study transthoracic echocardiograms.

Investigators can image as often as medically necessary or as needed based on their institution's standard-of-care; however, protocol-based imaging must be performed according to the timepoints noted in the Time and Events Schedule. Echocardiograms will be sent to a core laboratory for blinded reading and to minimize inter-site variability and bias. During the course of the study, for subjects who prematurely discontinue study drug for any reason, the final echocardiogram will be performed as soon as possible after discontinuation at the ESMD visit. A detailed description of the echocardiogram core laboratory process will be provided in a separate manual. The Post-Fontan Echocardiographic Examination protocol is provided in [Attachment 2](#).

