9.4. Efficacy Evaluations/Outcomes

The primary efficacy outcome will be any thrombotic event (venous or arterial), defined as:

- The appearance of a new thrombotic burden within the cardiovascular system on either routine surveillance or clinically indicated imaging, or
- The occurrence of a clinical event known to be strongly associated with thrombus (such as cardioembolic stroke, pulmonary embolism).

Subjects who develop either a symptomatic or asymptomatic thrombotic event during the study must permanently discontinue the study drug. All thrombotic events and the primary cause of any death will be adjudicated by the CIAC. Transthoracic echocardiograms will be centrally read by an echocardiographic core laboratory. All available imaging results (eg, transthoracic or transesophageal echocardiograms, or MRIs), should be sent to the CIAC. Sites will be required to complete a worksheet, compile an adjudication package, and send it to the adjudication office within 6 weeks from occurrence of the event.

After cessation of the study drug, it is at the investigator's discretion to continue with other antithrombotic therapy. The investigator should document this therapy in the eCRF. Thrombotic events will not be reported as adverse events or serious adverse events, as they will be reported as efficacy outcomes, which will be documented in the eCRF.

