10.2.2. Permanent Discontinuation of Study Drug

A subject's study treatment should be discontinued permanently if:

- The investigator believes that for safety reasons (eg, adverse event or persistent noncompliance) it is in the best interest of the subject to discontinue study treatment
- The subject has a thrombotic event
- The subject develops any condition that requires treatment with anticoagulant or antiplatelet therapy
- The subject has a major bleeding event, eg, intracranial bleeding (for definitions of major bleeding see Section 9.3.1, Bleeding Events)
- The subject, his or her parents/legally acceptable representatives request to discontinue the study drug permanently

For subjects in Part A and Part B who prematurely and permanently discontinue the study drug for any reason, the ESMD visit will be performed as soon as possible after discontinuation of the study drug. A Follow-Up phone contact will be performed 30 days following the last dose of the study drug. In addition, an ESMD Month 12 Follow-Up phone contact will be conducted at the end of the planned treatment period. This excludes subjects who are enrolled after local reading of the Screening transthoracic echocardiogram rules out thrombosis, and subsequently reported to have thrombosis after central reading by the core laboratory of the same transthoracic echocardiogram. These subjects will be withdrawn from the study when the result of the echocardiogram by the core laboratory becomes available. Subjects will be asked to return for

the ESMD visit as soon as possible. They will not be required to have a repeat transthoracic echocardiogram as part of the ESMD. Subjects will go on to receive proper care according to the healthcare provider's judgment. They will be contacted by phone approximately 30 days (+/- 7 days) after last dose of study drug (Follow-Up Contact). An ESMD Month 12 follow up visit will not be required.

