## **2.3 Analysis Periods**

On-Treatment Period: This analysis period includes all data from the first dose of study drug to 2 days after the last dose of the study drug administration (inclusive).

Up-to-End-of-Treatment Period: This analysis period includes all data from first dose to end of treatment visit (i.e., last efficacy-evaluation date - Month 12 or ESMD visit)

Up-to-Last-FU (last contact): This analysis period includes all data from first dose to trial reference end date.

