### **3.4 Treatment Compliance**

Rivaroxaban will be administered twice daily in an open-label fashion. Rivaroxaban will be taken in the morning and in the evening (approximately 12 hours apart) as described in study booklet.

Subjects randomized to ASA will receive approximately 5 mg/kg as a single dose. ASA will be provided as tablets according to the local practices.

Dose adjustments due to increased body weight will be made at Month 6 for subjects in Parts A and B for both rivaroxaban and ASA.

IWRS will keep track of study drug dispensed to subjects in both Part A and Part B. Study drug accountability will be performed at each visit.

For each subject, the treatment compliance rate is estimated as follows

Compliance rate (%) =  $100 * \text{actual treatment duration} / \text{intended treatment duration}$

More specifically, the actual treatment duration will be calculated by minimum of [Day 353 date, last dose date, death date, and the first primary efficacy outcome date] - first dose date + 1 - dose interruption days. The intended treatment duration will be calculated by minimum of [Day 353 date, death date, and the first primary efficacy outcome date] - first dose date + 1 - dose interruption days due to the reasons specified in protocol 10.2.1 (for example, bleeding, and other AEs).

Compliance rate will be summarized by treatment group.

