### **3.6 Protocol Deviations**

Major protocol deviations will be summarized by treatment group. The categories of protocol deviations may include, but are not limited to the following:

- Not meeting key inclusion or exclusion criteria
- Taking incorrect study drug
- Not discontinuing study drug permanently according to the protocol
- Having been taking prohibited concomitant therapies as specified in the protocol

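### The Per-protocol Set drops a child who stays on study drug after a confirmed thrombus, so an on-treatment primary event is lost from the optional Per-protocol summary

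*SAP*

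**What the plan says.** SAP 2.2 forms the Per-protocol Set by taking whole subjects with key deviations out of the Full Analysis Set. One listed deviation is "Not discontinuing study drug permanently according to the protocol". No date limit or event cutoff is attached to it.

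Protocol 9.4 makes any thrombotic event the primary efficacy outcome and adds: "Subjects who develop either a symptomatic or asymptomatic thrombotic event during the study must permanently discontinue the study drug". SAP 5 repeats both statements. Protocol 10.2.2 lists among its triggers for permanent discontinuation: "The subject has a thrombotic event".

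SAP 5 allows, but does not require, an efficacy summary on the Per-protocol Set over the On-Treatment Period. SAP 2.3 runs that period "from the first dose of study drug to 2 days after the last dose of the study drug administration", inclusive. The estimator is children with an event divided by children at risk at the start of the period, with a 95% CI, plus Kaplan-Meier estimates of time to first event.

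The main efficacy description uses the Full Analysis Set (less children whose screening echocardiogram is centrally read as showing thrombosis) and CIAC-confirmed outcomes. On testing, SAP 1.3 states: "There is no formal hypothesis testing for this study".

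**The concern.** Through the thrombosis trigger, a child can commit this deviation only after a thrombus has been diagnosed. When the CIAC confirms the event, the exclusion is therefore selection on the outcome. Of two children with the same on-treatment thrombus, the one who stops is counted and the one who continues is not. Dosing after the first event cannot have affected whether or when that event occurred, yet it decides whether the event is counted.

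At stake is the accuracy of one supportive summary. An on-treatment analysis exists to count thrombi that arise on treatment, and this rule can delete one of them. In arms of about 60 and 30 children with few events, one deletion is visible in the reported proportion.

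**Working it through.** **Step 1: does the rule reach a valid event?**

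- *Exclusion unit:* the whole subject, not the time after the deviation (SAP 2.2).
- *Trigger:* a thrombotic event, which is also the primary outcome (Protocol 9.4 and 10.2.2; SAP 5).
- *Timing:* if dosing continued after the thrombus, the event precedes the last dose. It therefore lies inside the On-Treatment Period (SAP 2.3), the period paired with the Per-protocol Set in SAP 5.
- *Opportunity:* a thrombus can be recognized during planned treatment at the Month 6 echocardiogram or on other imaging. Protocol 9.1.6 says "Investigators can image as often as medically necessary".

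So a CIAC-confirmed event that the summary would otherwise count is removed from both numerator and denominator.

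**Step 2: inputs for size.** The documents give no figure on this point, so there is nothing to reproduce. Part B has about 90 children at 2:1, hence 90 × 2/3 = 60 rivaroxaban and 90 × 1/3 = 30 ASA. Pooling about 10 from Part A gives 60 + 10 = 70 rivaroxaban. Event counts k are assumptions. No other Per-protocol exclusions are assumed.

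**Step 3: formula for a confirmed event.** Removing one child turns k/n into (k−1)/(n−1). The fall is

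k/n − (k−1)/(n−1) = (n−k) / [n(n−1)],

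which is positive whenever k < n. For k = 2, n = 60: 58/3540 = 1.64 points. For k = 3, n = 30: 27/870 = 3.10 points.

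| Arm | Event counted (exact 95% CI) | Child dropped (exact 95% CI) | Fall, points |
|---|---|---|---|
| Rivaroxaban, Part B | 1/60 = 1.67% (0.04 to 8.94) | 0/59 = 0% (0 to 6.06) | 1.67 |
| Rivaroxaban, Part B | 2/60 = 3.33% (0.41 to 11.53) | 1/59 = 1.69% (0.04 to 9.09) | 1.64 |
| Rivaroxaban, Part B | 6/60 = 10.00% (3.76 to 20.51) | 5/59 = 8.47% (2.81 to 18.68) | 1.53 |
| Rivaroxaban, pooled | 2/70 = 2.86% (0.35 to 9.94) | 1/69 = 1.45% (0.04 to 7.81) | 1.41 |
| ASA | 3/30 = 10.00% (2.11 to 26.53) | 2/29 = 6.90% (0.85 to 22.77) | 3.10 |

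**Step 4: between-arm difference (rivaroxaban minus ASA).** Start from 2/60 − 3/30 = −6.67 points.

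- Child lost from rivaroxaban: 1/59 − 3/30 = −8.31 points.
- Child lost from ASA: 2/60 − 2/29 = −3.56 points.

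The difference can move either way.

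**Step 5: trigger later refuted.** If failure to stop is judged on a local diagnosis that the CIAC does not confirm, the child removed may have no counted event. Then k/n becomes k/(n−1), a rise of k/[n(n−1)]. For k = 2, n = 60: 2/59 = 3.39%, up 2/3540 = 0.06 points.

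**The case against.** **The scenario may never occur.** It needs a child kept on drug after a recognized thrombus, against an instruction stated repeatedly in both documents. Neither document gives a frequency. This stands. A reader might extend the point to doses given before a silent thrombus is recognized, but the SAP does not say that such dosing counts as the deviation.

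**The harm is contained.** This also stands. The summary is optional and nothing is tested. The Full Analysis Set description keeps the event, SAP 5 lists efficacy outcomes, and SAP 3.6 says "Major protocol deviations will be summarized by treatment group", naming this category. That limits the weight of the point but does not make the set definition right if the summary is produced.

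**The proportion need not fall.** A reader might infer that every exclusion through this trigger removes an event. The documents do not support that. The counted outcome is CIAC-confirmed, while neither document says whether the stop duty is judged on the local, core laboratory or CIAC reading. Step 5 shows the opposite direction.

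**Other deviations.** A reader might want all post-baseline deviations ignored once an event has occurred. That goes too far. A child with an event at Month 6 and prohibited therapy at Month 9 would stay in, while an event-free child with the same Month 9 deviation would be excluded, so the deviation window would itself depend on the outcome.

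**The Data Presentation Specifications may settle it.** They are a separate document not available here. SAP 1 assigns analysis-set definitions to the SAP and describes the specifications as titles, mock-ups and programming instructions. They could still contain a timing rule, so the gap is shown for the SAP only.

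**Conclusion.** The point holds, is minor in severity, and is a cheap improvement. As written, SAP 2.2 would drop a child with a valid on-treatment primary event because of conduct after it. For a CIAC-confirmed event, each such removal lowers that arm's Per-protocol proportion, by about 1.5 to 1.7 points on Part B rivaroxaban and about 3 points on ASA in the cases worked. These shifts are small against the interval widths.

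The size rests on assumed event counts, planned arm sizes and no other Per-protocol exclusions. It is nil if every child stops as required.

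Two stronger readings are not supported. The rule does not bias the trial's main efficacy description, which uses the Full Analysis Set. Nor does it systematically favor rivaroxaban, because the difference moves according to which arm loses the child. The compliance formula in SAP 3.4, which ends intended treatment no later than the first primary outcome, does not contradict SAP 2.2 either. It serves another purpose and shows only that the SAP already uses that date.

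**What to change.** Add to SAP 2.2:

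> Failure to discontinue study drug after a CIAC-confirmed thrombotic event is not by itself a reason for exclusion from the Per-protocol Set; the subject's first event is retained and counted, and the deviation is reported under Section 3.6.

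Leave the handling of other deviations and other stop triggers unchanged.

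The cost is one sentence, with no change to data collection, sample size or the main analysis. The downside is that the set may include children who stayed on drug after their event. That cannot affect a first-event incidence or a Kaplan-Meier estimate of time to first event. A child who continued after a local diagnosis that the CIAC refutes would be handled as now.
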